#### 9.1.3.4 Adverse Events of Special Interest

AESIs will be captured as SAEs and will be collected throughout the study. These include new onset of GBS, encephalitis / myelitis (including transverse myelitis), Bell's palsy, convulsions, optic neuritis, and brachial neuritis [\(25\)](#) [\(26\)](#) [\(27\)](#).

#### 9.1.3.5 Assessment of Causality

The Investigator will assess the *causal relationship* between each unsolicited systemic AE and the product administered as either *not related* or *related*, based on the following definitions:

Not related – The AE is clearly / most probably caused by other etiologies such as an underlying condition, therapeutic intervention, or concomitant therapy; or the delay

between vaccination and the onset of the AE is incompatible with a causal relationship; or the AE started before the first vaccination (screening phase, if applicable)

Related – There is a “reasonable possibility” that the AE was caused by the product administered, meaning that there is evidence or arguments to suggest a causal relationship

Note: By convention, all AEs reported at the injection site (whether solicited or unsolicited) and all solicited systemic AEs are considered to be related to the administered product and therefore are referred to as reactions and do not require the Investigator’s opinion on relatedness.

Adverse events likely to be related to the product, whether serious or not, that persist at the end of the study will be followed up by the Investigator until their complete disappearance or the stabilization of the subject’s condition. The Investigator will inform the Sponsor of the date of final disappearance of the event or the date of “chronicity” establishment.

## 9.2 Immunogenicity

### 9.2.1 Immunogenicity Endpoints

#### 9.2.1.1 Immunogenicity by HAI Method

The endpoints for the evaluation of immunogenicity by HAI method are:

***For subjects 9 to 17 years of age and previously influenza vaccinated subjects 6 months to 8 years of age:***

- HAI antibody (Ab) titers obtained on D0 and D28
- Individual HAI titers ratio D28/D0
- Seroconversion (titer < 10 [1/dil] at D0 and post-injection titer  $\geq$  40 [1/dil] at D28, or titer  $\geq$  10 [1/dil] at D0 and a  $\geq$  4-fold increase in titer [1/dil] at D28)
- Percentage of subjects with titers  $\geq$  40 (1/dil) at D0 and D28

***For previously influenza unvaccinated subjects 6 months to 8 years of age:***

- HAI Ab titers obtained on D0, D28, and D56
- Individual HAI titers ratio D28/D0 and D56/D0
- Seroconversion (titer < 10 [1/dil] at D0 and post-injection titer  $\geq$  40 [1/dil] at D28 and D56, or titer  $\geq$  10 [1/dil] at D0 and a  $\geq$  4-fold increase in titer [1/dil] at D28 and D56)
- Percentage of subjects with titers  $\geq$  40 (1/dil) at D0, D28, and D56

#### 9.2.1.2 Immunogenicity by Virus SN Method

The endpoints for the evaluation of immunogenicity by virus SN method are:

***For subjects 9 to 17 years of age and previously influenza vaccinated subjects 6 months to 8 years of age:***

- Individual neutralization test (NT) Ab titer on D0 and D28
- Individual NT Ab titer ratio (fold increase in serum NT post-vaccination relative to D0) at D28
- Subjects with NT Ab titers  $\geq 20$  (1/dil),  $\geq 40$  (1/dil),  $\geq 80$  (1/dil) at D28
- Fold-increase in NT Ab titer [post/pre]  $\geq 2$  and  $\geq 4$  at D28
- Detectable NT (NT Ab titer  $\geq 10$  [1/dil]) at D0 and D28

***For previously influenza unvaccinated subjects 6 months to 8 years of age:***

- Individual NT Ab titer on D0, D28, and D56
- Individual NT Ab titer ratio (fold increase in serum NT post-vaccination relative to D0) at D28 and D56
- Subjects with NT Ab titers  $\geq 20$  (1/dil),  $\geq 40$  (1/dil),  $\geq 80$  (1/dil) at D28 and D56
- Fold-increase in NT Ab titer [post/pre]  $\geq 2$  and  $\geq 4$  at D28 and D56
- Detectable NT (NT Ab titer  $\geq 10$  [1/dil]) at D0, D28, and D56

### **9.2.2 Immunogenicity Assessment Methods**

Assays will be performed by the Sponsor's laboratory (GCI, Swiftwater, PA, USA) or at an external testing laboratory under GCI supervision. The address is provided in the Operating Guidelines.

#### ***Anti-Influenza Virus Ab Titration by Inhibition of Hemagglutination***

Test serum samples and quality control sera (sheep, ferret, and/or human sera) are incubated with Sigma Type III neuraminidase from vibrio cholerae to eliminate non-specific inhibitors. Adsorption of spontaneous anti-species agglutinins is then performed by incubating the test serum samples and quality control sera with a red blood cell (RBC) suspension. Following this, the mixtures are centrifuged and the supernatants containing the treated sera are collected for testing. Ten two-fold dilutions (starting at 1:10) of the treated test serum samples and quality control sera are incubated with a previously titrated influenza antigen at a concentration of 4 hemagglutination unit (HAU)/25  $\mu$ L. Influenza antigen is not added to the serum control wells containing only serum and RBCs. The mixture is then incubated and a RBC suspension is added. Following incubation, the results are read. The endpoint of the assay is the highest serum dilution in which complete inhibition of hemagglutination occurred. Each serum sample is titrated in two independent assay runs, and the 2 values, which cannot differ by more than 1 two-fold dilution, are reported. The GMT between the 2 values is calculated at the time of statistical analysis. The lower limit of quantitation (LLOQ) is set at the lowest dilution used in the assay, 1:10. Titers below this level are reported as  $< 10$  (1/dil). If the lowest / first serum dilution used in the assay exhibits complete inhibition of hemagglutination, the serum Ab titer will be reported as  $< 10$  (1/dil). If the highest / last serum dilution used in the assay exhibits complete inhibition of hemagglutination, the serum Ab titer will be reported as  $\geq 10240$  (1/dil).

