### ***Influenza Virus Neutralization Test***

Assays will be performed by the Sponsor's laboratory (GCI, Swiftwater, PA, USA).

This NT measures Abs directed against the viral neutralization epitopes of the influenza virus, which may be different from the hemagglutination epitopes, therefore, the NT titers may be different from the HAI titers.

To measure NT, serially diluted, heat-inactivated human serum samples will be pre-incubated with a fixed amount of challenge virus prior to the addition of Madin-Darby canine kidney (MDCK) cells. After overnight incubation, the viral nucleoprotein production in infected MDCK cells is measured by enzyme-linked immunosorbent assay (ELISA), using monoclonal Ab specific to either influenza A nucleoprotein or influenza B nucleoprotein. Since serum neutralizing Abs to the influenza virus inhibits the viral infection of MDCK cells, the ELISA optical density results are inversely proportional to the titers of neutralizing Ab present in the serum. The LLOQ is set at the reciprocal of the lowest dilution used in the assay, ie, 10 (1/dil). Titers below this level are reported as < 10 (1/dil). The highest titer that would be reported is 10239 (1/dil). Anything  $\geq$  10240 (1/dil) will be pre-diluted, retested, and end point titers will be reported.

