### 12.3.2 Immunogenicity

In order to appropriately manage replicate values for analysis purposes, the individual geometric mean of all values will be computed for each blood sample after managing extreme values as described. The computed value is then considered the titer for that particular blood sample.

- If a titer is  $<$  LLOQ, then the computed value, LLOQ/2, will be used.
- If a titer is  $\geq$  LLOQ and  $<$  upper limit of quantitation (ULOQ) (or  $\leq$  ULOQ), then the titer itself will be used.
- If a titer is  $\geq$  ULOQ (or  $>$  ULOQ), then computed value, ULOQ, will be used.

Any other replacement to be applied to specific endpoints will be described in the SAP.

Missing data will not be imputed. No test or search for outliers will be performed.

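### The HAI reporting rules in Protocol 9.2.2 contradict the assay description at both ends: complete inhibition at 1:10 is reported as <10, and ten two-fold dilutions from 1:10 end at 5120, not 10240

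*Protocol*

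**What the plan says.** All the conflicting statements are in one paragraph of Protocol Section 9.2.2, the HAI method.

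- Dilution series: "Ten two-fold dilutions (starting at 1:10) of the treated test serum samples" and of the control sera.
- End point: "The endpoint of the assay is the highest serum dilution in which complete inhibition of hemagglutination occurred".
- Lower limit: "The lower limit of quantitation (LLOQ) is set at the lowest dilution used in the assay, 1:10". Titers under it are reported as <10.
- Low-end rule: "If the lowest / first serum dilution used in the assay exhibits complete inhibition of hemagglutination, the serum Ab titer will be reported as" <10.
- High-end rule: "If the highest / last serum dilution used in the assay exhibits complete inhibition of hemagglutination, the serum Ab titer will be reported as" ≥10240.
- Duplicates: each serum is run twice, and "the 2 values, which cannot differ by more than 1 two-fold dilution, are reported".

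Protocol 12.3.2 and SAP 4.4.2.1 turn these reports into analysis values. Anything below the LLOQ becomes LLOQ/2, which is 5. For anything at or above the upper limit, "then computed value, ULOQ, will be used". Neither section gives a number for the HAI upper limit. SAP 4.2 refers back to Protocol 9.2 for the methods.

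**The concern.** At the low end, the rule assigns <10 to the very result that the end-point definition makes a titer of at least 10. At the high end, the stated ceiling is one doubling above the last dilution described. The seroneutralization text in the same section sets the same lower limit of 10 and has no comparable sentence, so it neither needs nor supports the HAI wording.

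Reported HAI values feed the LLOQ/2 and ULOQ substitutions, and through them the GMTs, the fold-rises, the 4-fold-rise indicator (SAP 4.4.2.2) and the baseline <10 / ≥10 split in the seroconversion definition (SAP 4.4.2.3). The study is meant to choose the Phase III dosage, and HAI serves two of its three immunogenicity objectives. Protocol Sections 3 and 9.2.2 also allow testing at an outside laboratory, so the written method should be correct on its own.

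**Working it through.** **High end.** The inputs are ten dilutions, factor 2, first dilution 1:10. Dilution k is 10 × 2^(k−1):

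10, 20, 40, 80, 160, 320, 640, 1280, 2560, 5120.

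The tenth is 10 × 2^9 = 5120, so the stated 10240 is not reproduced. It needs 10 × 2^10, an eleventh dilution, or ten dilutions starting at 1:20. If the last of ten dilutions is reported as ≥10240, the reportable scale goes from 2560 straight to ≥10240 and 5120 can never appear. End points of 2560 and 5120, one dilution apart, would be reported log2(10240/2560) = 2 steps apart, against a limit of one for the two reported values.

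**Low end.** A serum with titer 40 also inhibits completely at 1:10, so the literal rule reports it as <10. A serum that inhibits at every dilution meets both the <10 rule and the ≥10240 rule. The sentence cannot be applied as printed.

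To size the problem, take the narrowest reading: only end points of exactly 10 become <10. This reading is constructed for the calculation and is not stated in the plan. The duplicate pairs that contain a 10 and lie at most one dilution apart are:

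| Duplicates | Value under end-point definition | Value under narrow reading | Ratio | Post-vaccination titer needed to seroconvert |
|---|---|---|---|---|
| (<10, 10) | √(5×10) = 7.07 | √(5×5) = 5 | 1.41 | 40, then 40 |
| (10, 10) | 10 | 5 | 2.00 | 4×10 = 40, then 40 |
| (10, 20) | √(10×20) = 14.1 | √(5×20) = 10 | 1.41 | 56.6, then 40 |

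The third pair would be reported as (<10, 20), two steps apart. The protocol puts the one-dilution limit on the reported values, so this pair would not be accepted and is left out. On that basis no seroconversion status changes. No ≥40 status can change either, because a replicate of 10 pairs with at most 20 (geometric mean 14.1).

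The 4-fold-rise indicator can change. With a post-vaccination titer of 20:

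- A (10, 10) baseline goes from 20/10 = 2.0 to 20/5 = 4.0.
- A (<10, 10) baseline goes from 20/7.07 = 2.83 to 4.0.

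Both move from No to Yes. A (10, 10) baseline also crosses the <10 / ≥10 cut-off. It would change baseline-serostatus subgroup if the same cut-off is used there, which the SAP does not say.

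**Arm-level size.** The documents give no titer distribution, so every share below is an assumption.

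- Share f of baseline sera at (10, 10), with no post-vaccination sera affected. The baseline GMT factor is 2^(−f) and the fold-rise factor is 2^f. For f = 10%, 20%, 30% the GMT factor is 0.93, 0.87, 0.81 and the fold-rise factor is 1.07, 1.15, 1.23. Post-vaccination sera at (10, 10) would reduce the fold-rise shift.
- Difference d between arms in the share of post-vaccination (10, 10) sera. The GMT-ratio factor is 2^d. For d = 0, 2, 5 percentage points it is 1.000, 1.014, 1.035.
- Share p of an arm's sera with the last dilution, 1:5120, as end point in both runs but analysed as 10240. Each is a factor 2.00 (log10 2 = 0.30) above the 5120 that the series supports, and the GMT factor is 2^p. For p = 0.5%, 1%, 2% it is 1.003, 1.007, 1.014. If the last dilution is really 1:10240, there is no effect.

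**The case against.** The strongest reply is that this is an editorial slip nobody would act on. The sentence just before the faulty one gives the right low-end rule, the SAP uses any value at or above the LLOQ as it stands, and the literal reading is absurd. The laboratory validates its data under its own procedures (Protocol 11.2), its staff are blinded to product (Protocol 6.4), and all analyses are descriptive. This stands as an argument that the effect is small and falls on both arms alike. It does not make the printed rule usable.

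At the high end, the series could mean ten doublings after a 1:10 start, which does reach 10240, the only upper HAI figure in the documents. That reading is strained: the paragraph starts its ten dilutions at 1:10 and calls 1:10 the lowest dilution used. It does show that the error may lie in the dilution count and not in the limit.

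A third point concerns the duplicate limit. If it applies to raw end points before conversion to <10, the (10, 20) baseline stays in. A post-vaccination titer of 40 is then a 2.8-fold rise under the correct rule and a 4-fold rise under the faulty one, so seroconversion could flip. On the same view, end points of 2560 and 5120 would not breach the limit. The protocol speaks of the two values as reported, which supports leaving the pair out, but the conclusion that seroconversion is untouched depends on that reading.

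**Conclusion.** The concern holds. The low-end rule contradicts the end-point definition and the LLOQ under any reading. That a *not* was lost is an inference, but the contradiction is not. On the plain wording, the high-end figure is one doubling above the last dilution, and nothing in the protocol or SAP shows whether the count or the limit is wrong.

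An affected titer would be off by a factor of up to 2. On the narrow low-end reading, fold-rises and the 4-fold-rise indicator are exposed, while seroconversion and ≥40 status are not, provided the duplicate limit applies to reported values. Between-arm GMT ratios would move much less than fold-rises. The laboratory probably applies the correct rule, so the practical effect is likely small. The governing text is still wrong as written, and the upper limit that the SAP's substitution rule needs is unsettled. It should be corrected, but it does not threaten the study's conclusions.

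**What to change.** 1. In Protocol 9.2.2, report <10 when the first dilution (1:10) fails to inhibit hemagglutination completely.
2. Check the dilution count and the ceiling against the laboratory method and make them agree: ten dilutions with ≥5120, or eleven with ≥10240.
3. State the numeric HAI LLOQ (10) and the confirmed ULOQ in SAP 4.4.2.1.

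The cost is one sentence and one reconciled figure in the protocol and two numbers in the SAP. No extra testing is needed.

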### ***Influenza Virus Neutralization Test***

Assays will be performed by the Sponsor's laboratory (GCI, Swiftwater, PA, USA).

This NT measures Abs directed against the viral neutralization epitopes of the influenza virus, which may be different from the hemagglutination epitopes, therefore, the NT titers may be different from the HAI titers.

To measure NT, serially diluted, heat-inactivated human serum samples will be pre-incubated with a fixed amount of challenge virus prior to the addition of Madin-Darby canine kidney (MDCK) cells. After overnight incubation, the viral nucleoprotein production in infected MDCK cells is measured by enzyme-linked immunosorbent assay (ELISA), using monoclonal Ab specific to either influenza A nucleoprotein or influenza B nucleoprotein. Since serum neutralizing Abs to the influenza virus inhibits the viral infection of MDCK cells, the ELISA optical density results are inversely proportional to the titers of neutralizing Ab present in the serum. The LLOQ is set at the reciprocal of the lowest dilution used in the assay, ie, 10 (1/dil). Titers below this level are reported as < 10 (1/dil). The highest titer that would be reported is 10239 (1/dil). Anything  $\geq$  10240 (1/dil) will be pre-diluted, retested, and end point titers will be reported.

### **9.3 Efficacy**

No clinical efficacy data will be obtained in the study.

## **10 Reporting of Serious Adverse Events**

To comply with current regulations on SAE reporting to health authorities, the Investigator must document all SAEs regardless of causal relationship, and notify the Sponsor and the Clinical Research Associate (CRA) within the notification timelines stated in the following sections. The Investigator will give access and provide the Sponsor and the CRA with all necessary information to allow the Sponsor to conduct a detailed analysis of the safety of the investigational products. It is the responsibility of the Investigator to request all necessary documentation (eg, medical records, discharge summary, autopsy) in order to provide comprehensive safety information. All relevant information must then be transcribed onto the AE CRF and the appropriate Death/Safety Complementary Information CRFs.

### **10.1 Initial Reporting by the Investigator**

Serious adverse events occurring during a subject's participation in the study or experiment must be reported within 24 hours to the Sponsor's GPV Department and to the CRA. Every SAE must be reported, even if the Investigator considers that it is not related to the vaccine. The investigator (licensed physician [M.D. or D.O.]) must validate the information entered on the AE CRF by completing the investigator validation form.

The Investigator must indicate on the AE CRF that the event was serious and must complete the relevant SAE section of this form as well as the appropriate Death/Safety Complementary

Information CRFs. An e-mail alert will automatically be sent by the EDC system to the GPV mailbox, the CRA and the CTL with relevant SAE information details.

If the EDC system is unavailable, the site must notify the Sponsor, using the paper version of the CRB, as described in the operating guidelines:

The Investigator must complete the paper copies of the AE CRF and of the appropriate Death/Safety Complementary Information CRFs and send them to the Sponsor by one of the following means:

- By fax, to the following number: [contact]
- In PDF format to the following e-mail address, using a method of transmission that includes password protection: [contact]
- By express mail, to the following address:

Global PharmacoVigilance, Sanofi Pasteur  
[name]  
[name]

When the EDC system becomes available, the Investigator must transcribe the information from the paper forms into the EDC system.

If there is need for urgent consultation, the Investigator is to contact the RMO. If the RMO cannot be reached, the Investigator may contact the Call Center as described in [Section 5.2.12](#).

## 10.2 Follow-up Reporting by the Investigator

The AE CRF completed initially must be updated within 24 hours after the Investigator has become aware of any new relevant information concerning the SAE (eg, outcome, precise description of medical history, results of the investigation). All relevant information must be included directly in the AE CRF and the appropriate Death/Safety Complementary Information CRFs. An e-mail alert will be sent automatically to the GPV Department and to the CRA. Copies of documents (eg, medical records, discharge summary, autopsy) may be requested by the GPV Department.

The anonymity of the subject must always be respected when forwarding this information.

## 10.3 Reporting of SAEs Occurring After a Subject Has Completed the Study

Any SAE that occurs after a subject has completed the study but that is likely to be related to the investigational products, or to the experiment must also be reported as soon as possible. In such a case, the reporting procedure to be followed is identical to that described in [Section 10.1](#).

## 10.4 Assessment of Causality

The causal relationship between the SAE and the product administered will be evaluated by the Investigator as described in [Section 9.1.3.5](#).

Following this, the Sponsor's Global Safety Officer (GSO) will also assess the causal relationship to the product, based on the available information and current medical knowledge.

The causal relationship to study procedures will be also assessed in the CRB.

The decision to modify or discontinue the study may be made after mutual agreement between the Sponsor and the Investigator(s).

## 10.5 Reporting SAEs to Health Authorities and IECs / IRBs

The Sponsor will inform the relevant health authorities of any reportable SAEs according to the local regulatory requirements. Reporting to the health authorities will be according to the Sponsor's standard operating procedures.

The Sponsor's RMO ([name], CTL) will notify the Investigators in writing of the occurrence of any reportable SAEs. The Investigators / Sponsor will be responsible for informing the IECs or IRBs that reviewed the study protocol.

# 11 Data Collection and Management

## 11.1 Data Collection and CRB Completion

Individual diary cards, specifically designed for this study by the Sponsor and provided to the study sites, will be given to study participants for the recording of daily safety information as described in [Section 9.1.3](#). These diary cards will include prelisted terms and intensity scales (see [Table 9.1](#), [Table 9.2](#), [Table 9.3](#), [Table 9.4](#), and [Table 9.5](#)) as well as areas for free text to capture additional safety information or other relevant details. Subjects / parents / guardians will also be provided with rulers for measuring the size of injection site reactions, and with standard digital thermometers for measuring daily temperatures. To ensure consistency of reporting, the study sites will instruct subjects / parents / guardians on how to correctly use these tools.

The 6-month follow-up will be done by interviewing subjects / parents / guardians over the telephone using a questionnaire to capture SAEs and AESIs, if applicable. A memory aid will be provided to the subjects at the preceding study visit to help them record information on events occurring between this visit and the 6-month follow-up.

Relevant information will be transcribed into the AE CRF. Any SAEs captured during this 6-month follow-up period will be reported and followed-up as per the normal process for reporting SAEs.

At specified intervals, the Investigator or an authorized designee will interview the subjects / parents / guardians to collect the information recorded in the diary card, and will attempt to clarify anything that is incomplete or unclear. All clinical study information gathered by the study site will be reported electronically by the Investigator or authorized designee using a web-based CRB. (Any information that was not documented in the diary card will first be captured in the source document and then reported electronically.) The CRB has been designed specifically for this

study under the responsibility of the Sponsor, using a validated Electronic Records / Electronic Signature-compliant platform (21 CFR Part 11).

To ensure the correct and consistent completion of the CRBs, the Sponsor or authorized representative will provide all necessary tools, instructions, and training to all site staff involved in data entry prior to study start. Additional instructional documents such as training manuals and completion instructions will be provided to assist with data entry during the course of the study.

Upon completion of training, each user requiring access to the EDC system will be issued a unique username and password. In the event of a change in study personnel, each newly assigned individual will receive a unique username and password; the username and password of a previous user may not be reissued. If any study personnel leave the study, the Investigator is responsible for informing the Sponsor immediately so that their access is deactivated. An audit trail will be initiated in the EDC system at the time of the first data entry to track all modifications and ensure database integrity.

The Investigator is responsible for the timeliness, completeness, and accuracy of the information in the CRBs; must provide explanations for all missing information; and must sign the CRB using an e-signature.

